**Humalog®**

Please refer to the Summary of Product Characteristics [10] (if Europe sourced) or US prescribing information [11] (if US sourced) for Humalog® storage instructions.

Humalog® should not be used after the expiration date. Unopened HUMALOG should be stored in a refrigerator (36° to 46°F [2° to 8°C]), but not in the freezer. Do not use HUMALOG if it has been frozen. In-use HUMALOG KwikPen should be stored at room temperature, below 86°F (30°C) and must be used within 28 days or be discarded at the end of the study based on the Sponsor instructions, even if they still contain HUMALOG. It should be protected from direct heat and light (Table 1).

**Table 1: Humalog Kwikpen Usage Instructions**

	Not In-Use (Unopened) Room Temperature (Below 86°F [30°C])	Not In-Use (Unopened) Refrigerated	In-Use (Opened) Room Temperature, (Below 86°F [30°C])
3 mL Humalog KwikPen (prefilled)	28 days	Until expiration date	28 days, do not refrigerate.

### **5.5 Drug Accountability**

The sponsor will supply sufficient quantities of the investigational product to allow completion of this extension trial. Upon receipt of the investigational product supplies at the site, the designated trial staff member should count and verify that the shipment contains all the items noted in the shipment inventory.

The Investigator or designated staff must notify the monitor if there was a temperature deviation during shipment to the site (if information is available) or if the products are in any way damaged (Temp Tale® information should ensure accurate temperature monitoring). The Investigator or designee should temporarily quarantine compromised drug until notified by the monitor of actions to be taken (release for use or permanent quarantine for return and destruction). The monitor must notify the sponsor of any temperature deviations or damaged products. The sponsor or designee will assess the extent of the temperature deviation or damage and will inform the monitor in writing whether the product may be used or not.

The Investigator must keep complete and accurate records for the receipt, storage, dispensing, and return or destruction of investigational products and mealtime insulin.

### **5.6 Dispensing**

It is the responsibility of the Investigator to ensure that investigational products and mealtime insulin are dispensed only to trial patients. The Investigator or designee will dispense the required number of investigational product doses to ensure that the trial patient has sufficient supplies until the next dispensing visit.

Patients will be requested to return all used and unused medications to the site at each visit. The usability of the returned medications will be assessed. Returned medications may be again dispensed to the same patient, provided it was stored as per specification and will not cross the expiry date before the next visit.

The site will store the returned medication until the monitor has performed accountability and informs the site of the processes for destruction or return of the medication.

### **5.7 Administration**

Insulin glargine should be administered as a subcutaneous injection. It should be taken at approximately the same time every day. The preferred site is in the abdomen. The other possible sites of administration are the upper arm and thigh (upper leg). The injection sites should be rotated to reduce risk of lipodystrophy. Refer to the Investigator's Brochure [6] and US prescribing information [7]. Insulin lispro will be administered as per the Investigator's advice and as per the prescribing information [10,11].

The dosage of insulin will be adjusted based on SMBG profile, performed by the patients at home, so that patients attain the following glycemic targets (ADA 2014 criteria) [4]:

- Fasting pre-prandial SMBG between 70 to 130 mg/dL (3.9-7.2 mmol/L)

If the measured SMBG is <70 mg/dL (3.9 mmol/L) or if the patient has symptoms suggestive of hypoglycemia, he/she can call the Investigator or designee, if required. The insulin dose will be altered by the Investigator or designee, if required, based on the values. Any increase in total insulin dose per day of >6 units during any titration step should be performed with caution.

### **5.8 Return of Study Drug**

After the completion of the extension study, the monitor will perform the final drug accountability check and inform the site of the return/destruction procedures for the unused and partly used medication.

### **5.9 Treatment Compliance**

All reasonable and appropriate methods will be used to ensure compliance to the protocol for administration of trial medication.

### **5.10 Concomitant Medication**

Other than study drugs, insulin, insulin analogs and other anti-diabetes medications as well as glucocorticoid therapy (oral, intravenous, inhaled or other routes that produce systemic effects) should not be taken during the study (prohibited medications). A list of restricted

medications that may interfere with insulin is given in Table 2. No drugs listed in this table should be started during the treatment period.

**Table 2: Medications That Are Likely to Interfere with Diabetes Control**

Drug classes that are known to augment the blood glucose lowering effect of insulin such as:	Drugs and drug classes that are known to decrease the blood glucose lowering effect of insulin such as:

 
1. salicylates at doses more than >2 g/day
 
2. sulfa antibiotics
 
3. angiotensin converting enzyme inhibitors
 
4. disopyramide
 
5. fibrates
 
6. fluoxetine
 
7. monoamine oxidase inhibitors
 
8. propoxyphene
 
9. pentoxifylline
 
10. somatostatin analogs
 
11. bromergocryptine (bromocryptine)
 
12. anabolic steroids.
 
	
 
1. danazol
 
2. niacin
 
3. diuretics
 
4. sympathomimetic agents
 
5. glucagon
 
6. isoniazid
 
7. somatropin
 
8. thyroid hormones
 
9. oral contraceptives
 
10. estrogens
 
11. progestogens
 
12. protease inhibitors
 
13. phenothiazine derivatives
 
14. atypical antipsychotic medications (e.g. olanzapine and clozapine).
 

All treatments being taken by the patients following signing the ICF in addition to the trial treatment (investigational products and mealtime insulin) during the trial are regarded as concomitant medications and must be documented in the CRF. Mylan’s insulin glargine, Lantus® and insulin lispro will not be considered as concomitant medications.

## 6. STUDY PROCEDURES

This trial includes randomized comparative treatment period-1, randomized comparative treatment period-2, randomized comparative treatment period-3 and a follow-up period. Specific activities involved in each period are described in the SCHEDULE OF ACTIVITIES.

Throughout the trial, every reasonable effort should be made to follow the timing of assessments and procedures for each patient. Deviations from the schedule should be avoided. The allowed time window for each visit is shown in the SCHEDULE OF ACTIVITIES.

### 6.1 Visit Schedules and SMBG Profiles

Table 3 shows the SMBG profiling requirements at each visit.

**Table 3: SMBG Profile Requirements by Visit**

	Weeks 0 to 36	Week 40 (FU)
Mandatory clinic visit with 3 day 8-point SMBG in the week preceding the visit	Week 0 to week 36 visits	-
Telephone visit	As advised by the Investigator	SMBG will be performed for FU visit, as suggested by the Investigator at Week 36 visit (EOT)*

\*Additional visits or profiles to be performed as advised by the Investigator  
EOT: end of treatment; FU: follow-up visit; SMBG: self-monitored blood glucose.

## 6.2 Patient Withdrawal

If, for any reason, a patient discontinues the trial prematurely, the patient may be followed up upon consent and as described in the following withdrawal criteria:

Following are the withdrawal criteria:

1. Withdrawal of consent.
2. For female patients, diagnosis of pregnancy or stated intention to become pregnant. Effort should be made so that the pregnant women still report to the site and are followed until delivery or termination.
3. Repeated protocol non-compliance.
4. At the investigator's discretion (following discussion with the sponsor medical monitor), for safety issues such as severe hypoglycemia or hypoglycemic unawareness. The site should follow-up these patients as per the SCHEDULE OF ACTIVITIES until the 40 week follow-up call.
5. At the investigator's discretion, (following discussion with the sponsor medical monitor), in certain situations such as significant intercurrent illness, hospitalization for surgery, or an SAE. The site should follow-up these patients as per the SCHEDULE OF ACTIVITIES until the 40 week follow-up call.

Investigators must attempt to contact patients who fail to attend scheduled visits (by telephone or other means), to exclude the possibility of an AE being the cause of withdrawal. Should an AE be the cause for withdrawal, the AE must be documented, reported, and followed-up as described in Section 8. If withdrawal was not due to an AE the

Investigator should inquire about the reason for withdrawal. If applicable, request all withdrawn patients to bring back all unused investigational product(s) and return them at the final visit. The attempts to contact patients who fail to attend scheduled visits should be documented in the patient files as should the reasons for withdrawal.

No further evaluations should be performed, and no additional data should be collected if the patient withdraws from the trial and also withdraws consent for disclosure of future information. Data collected before patient withdrawal of consent will be retained and continue to be used, or destroyed if required per local regulation and rules.

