### ***9.2.2. Study Population***

The primary analysis will be based on the mITT population.

- The ITT population includes all randomized patients (including patients who receive incorrect treatment, do not complete the trial or do not comply with the protocol or used prohibited medication) and have baseline (week 0 visit) and at least one post-baseline value. ITT population will be used for secondary variable analyses.
- The mITT population includes all randomized patients (including patients who receive incorrect treatment, do not complete the trial or do not comply with the protocol or used prohibited medication) and have at least one baseline (week 0 visit) HbA1c value and one post-baseline HbA1c value at treatment period 3. The mITT will be used for primary analysis.
- Per Protocol (PP) population. The PP population includes patients who complete at least one baseline and one period 3 values and do not have protocol violations that impact the primary outcome. The subjects excluded from the PP population will be identified before database lock. PP population will be used for sensitivity analysis for primary variable.
- The safety population includes patients who take at least one dose of the trial medication. For safety analyses, patients will be categorized according to the treatment that they actually received. Safety population will be mainly used for safety population.

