5.4. MODIFIED INTENT-TO-TREAT POPULATION [MITT]

The mITT population includes all randomized patients (including patients who receive incorrect treatment sequence, do not complete the trial or do not comply with the protocol or used prohibited medication) and have at least one baseline (week 0 visit) HbA1c value and one post-baseline HbA1c value at treatment period 3 ($24 < \text{Week} \leq 36$). The mITT will be used for primary analysis.

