7.3. MISSING DATA

Missing primary and secondary efficacy and safety analysis data will be not imputed except when week 36 HbA1c data is missing due to early discontinuation, exit measurement of that period will be used for endpoint. In addition, for sensitivity analysis of multiple imputation method, if missing values occur in more than 10% of the patients for HbA1C values, then monotone regression for multiple imputations will be used.

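### Only two of the five withdrawal criteria direct scheduled follow-up, and no early-termination HbA1c is scheduled, so consenting patients can drop out of the primary analysis although their week-36 value was obtainable

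*Protocol*

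**What the plan says.** Protocol 6.2, repeated in the Synopsis, opens with a permissive rule for any early discontinuation: "the patient may be followed up upon consent and as described in the following withdrawal criteria". Five criteria follow.

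- Criteria 4 and 5 (investigator discretion, for safety issues or for events such as intercurrent illness or an SAE) each add: "The site should follow-up these patients as per the SCHEDULE OF ACTIVITIES until the 40 week follow-up call".
- Criterion 3 reads only "Repeated protocol non-compliance", with no follow-up instruction.
- Criterion 2 (pregnancy) adds: "Effort should be made so that the pregnant women still report to the site and are followed until delivery or termination". That concerns the pregnancy outcome, not the trial schedule.
- Criterion 1 is withdrawal of consent. The closing text of 6.2 bars further data collection if the patient also withdraws consent to future disclosure.

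The primary set is mITT. Protocol 9.2.2 requires that patients "have at least one baseline (week 0 visit) HbA1c value and one post-baseline HbA1c value at treatment period 3", and SAP 5.4 defines period 3 as after week 24 up to week 36. If week 36 is missing, SAP 15.1.2 uses the last non-missing period-3 value and imputes nothing else. SAP 7.3 says that, after early discontinuation, the "exit measurement of that period will be used for endpoint". The Schedule of Activities has visits V1 to V14, none of them for early termination, and shows HbA1c at weeks 0, 12, 24 and 36 only.

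**The concern.** The analysis plan presumes data that the protocol does not tell sites to collect. A patient withdrawn for non-compliance who is still willing to attend may, under 6.2, simply not be followed. That patient then has no period-3 HbA1c and leaves the primary analysis. The same applies to a patient who stops for a reason not on the list.

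Membership of the primary set therefore depends on an event after randomization, in a trial where patients and investigators know the assigned treatment. If the reasons for leaving, or the outcomes of those who leave, differ between the switching and continuous arms, the mITT comparison is no longer protected by randomization. In an equivalence trial such an error cannot be assumed to be conservative.

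**Working it through.** **1. The plan's own figure.** Inputs from Protocol 9.1, 9.2.6 and 9.7: margin ±0.4, SD 0.61, true difference 0, 69 randomized per arm, 10% without a baseline and last-period HbA1c, two-sided 95% CI.

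- Evaluable per arm: 69 × 0.90 = 62.1, taken as 62.
- SE = 0.61 × √(2/62) = 0.1096.
- Normal approximation: power = 2Φ(0.4/0.1096 − 1.96) − 1 = 2Φ(1.69) − 1 ≈ 90.9%.
- Exact t calculation: 90.4%.

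The stated 90% reproduces, so the sample size already allows for the planned loss.

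**2. Power by share without a period-3 HbA1c** (exact t, 69 randomized per arm, true difference 0):

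| Share lost | Power |
|---|---|
| 0% | 93.8% |
| 6.7% | 91.7% |
| 10% (plan) | 90.4% |
| 15% | 88.2% |
| 20% | 85.4% |

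**3. Follow-up by reason, against the need for a period-3 value.**

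| Reason | Follow-up in Protocol 6.2 | Week-36 HbA1c directed? |
|---|---|---|
| 1. Consent withdrawn | Barred if future disclosure is also refused | No; unavoidable in that case |
| 2. Pregnancy | Pregnancy outcome | No |
| 3. Non-compliance | Opening *may* only | No |
| 4 and 5. Investigator discretion | Schedule to week 40 | Yes |
| Unlisted reason | Opening *may* only | No |

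**4. The exit value.** Several sections presume an exit visit or its data: a final visit for returning product (Protocol 6.2), early discontinuation assessments in pregnancy (Protocol 8.4.1), an optional visit if the sponsor stops the trial (Protocol 15), and rules for early-termination or drop-out data (SAP 6.3, 7.3 and 15.2). None lists an HbA1c draw, and the Schedule has no column for the visit. Week 36 is the only scheduled period-3 sample, so the fallback in SAP 7.3 and 15.1.2 has no scheduled source.

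**5. A patient followed through the rules.** A consenting patient is withdrawn under criterion 3 at week 10. No instruction leads to a week-36 draw, so the patient is outside mITT. No post-baseline HbA1c has fallen due either, so the repeated-measures model has nothing from this patient. Under multiple imputation the later values would be filled in from baseline, arm and region. A patient who leaves at week 14 is also outside mITT, but the week-12 value does contribute to those sensitivity analyses.

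**6. What each remedy can recover.** The documents do not give the timing of withdrawals. If they were spread evenly over 36 weeks (assumption), one third would fall in period 3. An early-termination HbA1c alone would then cut a 10% loss to 10% × 2/3 = 6.7% (power 91.7%). Exits before week 24 stay outside mITT because their exit value is not in period 3. Follow-up to week 36 could recover up to the whole loss (93.8%). That is a ceiling, since patients who refuse further data collection cannot be recovered.

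**The case against.** The strongest reply is that the patients of most interest are already covered. Severe hypoglycemia, hypoglycemic unawareness, intercurrent illness and SAEs fall under criteria 4 and 5, whose follow-up includes the week-36 HbA1c. Some of the remaining loss is withdrawn consent, which no amendment can recover. SAP 15.1.4 also adds a repeated-measures model, and multiple imputation on ITT and PP. All of this stands and narrows the point to criteria 2 and 3 and unlisted reasons. It does not remove it. The added analyses are sensitivity analyses that model missing values from observed data, and SAP 7.3 can be read as using multiple imputation only when more than 10% of patients have missing HbA1c.

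The remedy is also open to challenge. Values drawn after study drug has stopped, or after a short period-3 exposure, may themselves pull the arms together. That stands, and the fix must deal with it.

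A reader might go further and infer a definite bias toward equivalence. For example, 10% missing times an assumed arm difference of 0.5 or 1.0 points among the missing gives 0.05 or 0.10. That could be set against an allowance of 0.40 − 1.98 × 0.1096 = 0.40 − 0.217 = 0.18. The documents do not support this:

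- The 10% (about 14 of 138) is all-cause. It includes consent withdrawals and any loss among criteria 4 and 5 patients. If a third of it arose from this gap (assumption), the figures fall to about 0.017 and 0.033.
- The 0.5 and 1.0 have no source in either document.
- The 0.18 is how large the observed difference can be before equivalence fails. It does not measure the risk of declaring equivalence wrongly.
- Neither document gives data linking withdrawal for non-compliance to glycemic outcome, so the sign is unknown.

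**Conclusion.** The gap is real but limited. As written, the plan can lose a primary outcome that was obtainable from a patient who still consents, and the SAP's exit measurement has no scheduled source. The affected patients are those withdrawn under criteria 2 and 3 and those with unlisted reasons. Their number is some unknown part of the planned all-cause loss of about 14, or more if loss exceeds plan.

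The documents allow neither the size nor the direction of any bias to be stated. There is no sample-size error: power is 90.4% at the planned loss and falls below 90% only if loss goes above about 10% (88.2% at 15%). These power figures rest on the plan's SD of 0.61 and a true difference of zero. The case for change is that it removes an avoidable selection from the primary set at little cost. It is not that the primary result would be invalid without it.

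**What to change.** These changes concern data collection and analysis only. They do not alter who is withdrawn or how any patient is treated.

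1. In Protocol 6.2 and the Synopsis, apply the follow-up sentence of criteria 4 and 5 to every withdrawal in which the patient still consents to data collection, with week-36 HbA1c as the minimum. This is the change that keeps patients in mITT.
2. Add an early-termination column with HbA1c to the Schedule of Activities, so that the SAP's exit measurement exists. State that it supplies a primary endpoint only for exits in period 3. Earlier exit values feed the ITT repeated-measures and multiple-imputation analyses.
3. Flag HbA1c drawn after study drug was stopped. Neither document says how such values are handled. Keep them in the mITT analysis, as values from criteria 4 and 5 patients already would be, and add a sensitivity analysis that excludes them. Report exits with short period-3 exposure alongside it.

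The cost is a short amendment, one added visit column, extra HbA1c samples for at most about 14 patients at the planned loss, and some off-drug values in the primary set.

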## **7. STUDY ASSESSMENTS AND METHODS**

### **7.1 Handling of Blood Samples**

Laboratory analysis will be conducted at central laboratories identified by the sponsor. The laboratory will provide specific sample kits to the Investigator site prior to the visit of patients. Instructions for collecting, handling, storing and shipping samples will be provided in the laboratory manuals.

### **7.2 Efficacy Assessments**

#### ***7.2.1. HbA1c***

HbA1c assessments will be performed as shown in the [SCHEDULE OF ACTIVITIES](#). The measurement will be performed by the central laboratory for safety and efficacy samples.

#### ***7.2.2. Fasting Plasma Glucose (FPG)***

FPG assessments will be performed as shown in the [SCHEDULE OF ACTIVITIES](#). The measurement will be performed by the central laboratory for safety and efficacy samples.

#### ***7.2.3. Body Weight and BMI***

Weight will be recorded by the site as specified in the [SCHEDULE OF ACTIVITIES](#). The Investigator will calculate the BMI (using the formula  $BMI = \text{weight in kg} / \text{height in m}^2$ ; for BMI calculation, the previous recorded weight will be used until new weight recording).

### 7.2.4. 8-point SMBG profiles

8-point SMBG profile measurements will be performed by the patient at home and recorded in the patient diary, as specified in the [SCHEDULE OF ACTIVITIES](#). One 8-point SMBG profile set includes measurements of SMBG values on 3 days, performed in the week preceding the next visit (of the three days, 2 should be consecutive). The time points for the 8-point SMBG are provided in Appendix III. The patient should document the 3 pre-visit measurements in the diary, and will be advised to similarly document any additional estimations.

On days in which SMBG is not mandated by protocol, patients will be advised to self-monitor their blood glucose 4 times a day.

### 7.2.5. Daily Insulin Doses

Patients will be asked to document the dose of Mylan’s insulin glargine/Lantus® and insulin lispro taken on the days when they perform 8-point SMBG profiles (from week 0 to week 24). Doses must be recorded in the patient diary. This data will be transcribed to the eCRF after the patient diary is collected, by the Investigator or designee. The patient should document the 3 pre-visit doses in the diary; and will be advised to document any additional doses.

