#### ***7.5.5. Patient Diary***

Patients will receive patient diaries as specified in the [SCHEDULE OF ACTIVITIES](#). The following will be recorded by the patient in the diary:

- Results of the 8-point SMBG measurements (on 3 days in the week before the next visit, of which 2 should be consecutive days)
- Mylan's insulin glargine/Lantus® and mealtime insulin doses on days where a 8-point SMBG is performed
- Hypoglycemic events experienced by the patient
- Adverse events experienced by the patient
- Disposable pen and needle -related issues

The Investigator will instruct the patient on the recording and measurement in detail of these assessments and will review the diary as specified in the [SCHEDULE OF ACTIVITIES](#). During review the Investigator should assess patient compliance with the trial procedures and based on the results of the 8-point SMBG check if a dose adjustment is required. The entries in the patient diary will be transcribed into the eCRF by the Investigator or designee.

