## **9.8 Secondary Efficacy Analyses**

In addition to the primary efficacy analysis for HbA1c, the following efficacy measures (both actual and change in values) will be summarized for each sequence at each post-baseline visits. Sequences will be compared using the MMRM ANCOVA model (similar to HbA1c analysis). The dependent variable will be the differences of change from baseline between two periods. The MMRM model will include the fixed, categorical effect of region and sequence group, visit, sequence group-by-visit interaction and the other as fixed effect terms region, and baseline value as covariates.

Descriptive statistical summaries for actual values and change from baseline will be displayed by visit and endpoint for each sequence group. ITT population will be applied to secondary efficacy analyses.

- Fasting plasma glucose;
- SMBG value: individual pre-meal, individual post-meal, individual 2-hour excursion after meal, bedtime, overall (average) pre-meal, overall post-meal, overall excursion, 4-point average (pre-meal + bedtime), and daily average;
- Daily prandial insulin, basal insulin, and total insulin dose (U/kg) for days of 8-point profiles.

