#### **Appendix IV - Sample Patient Diary Information**

- Trial, site and patient identification information
- Results of 8-point SMBGs performed as per protocol
- Insulin dose information on days where 8-point SMBGs are performed
- Details of hypoglycemic events
- Details of untoward experiences (AEs)
- Details of problems with the disposable pens or needles

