2.2. SECONDARY OBJECTIVES

To compare treatment sequence group of Mylan's insulin glargine to Lantus®, at 36 weeks, when administered in combination with mealtime insulin lispro with respect to:

1. Change in basal insulin dose per unit body weight (U/Kg/day).
2. Immunogenicity: incidence and change from baseline in the relative levels of ADA, incidence and change from baseline in the relative levels of anti-HCP antibodies.
3. Rate of hypoglycemic events per 30 days; and occurrence of hypoglycemia
4. Occurrence of local reactions, systemic reactions and other adverse events.
5. Change in fasting plasma glucose from baseline.
6. Change in 8-point (self-monitored blood glucose) SMBG profile from baseline
7. Device related safety assessment.

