applicable for morning excursion, noon excursion and evening excursion on the respective days. For overall excursion at morning, afternoon and evening, the individual excursion values obtained on each day will be averaged across three days.

For 4-point average, pre-meal and bedtime SMBG measurements will be averaged for a particular day and then this average value will be averaged across three days.

15.2.1.4. Daily insulin dose/unit body weight (daily prandial injectable, basal insulin and total) for days of 8-point profiles

Patients will be asked to document the dose of Mylan's insulin glargine/Lantus® and insulin lispro taken on the days when they perform 8-point SMBG profiles (from week 0 to week 36). Doses will be recorded in the patient diary. This data will be transcribed to the eCRF after the patient diary is collected, by the investigator or designee at scheduled visits. The patient should document the 3 pre-visit estimations in the diary; and will be advised to document any additional estimations.

There will be three dose variables – daily prandial insulin, basal insulin dose and total insulin dose.

Daily prandial insulin dose (meal time insulin dose) per day is the sum of all the daily prandial insulin dose for a day and then averages for number of days measured.

Basal insulin dose is the average of the insulin glargine or insulin Lantus dose over days measured. If the basal insulin dose is missing for a particular day of collection, total insulin dose will not be computed for that day. The total insulin dose will be computed for the remaining days were basal insulin dose is collected. The total insulin dose available at the remaining days will be used for the computation of average total insulin dose. For the computation of total daily prandial doses, the patients with at least three daily prandial doses at a particular day are considered. Total daily prandial dose will not be computed for a day if the daily prandial dose is recorded less than 3 times in a day and the total daily prandial dose computed at the remaining days will be used for the computation of average total daily prandial dose across the days.

Total insulin is the sum of daily prandial and basal insulin and then averaged for days measured. The missing insulin doses will not be considered for the average computation. All dose will be divided by total body weight (kg) to convert to daily insulin dose (U)/unit body weight (kg).

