Regression plots will be produced to assess the consistency of results obtained between the two assay types, and the regression plots will be produced for Total Insulin Antibody, Cross Reactive Insulin Antibody and Insulin (Drug) Specific Antibody by treatment sequence group.

The incidence of patients with increase over 10% cross reacting antibody increase in both assays, of HbA1c over 0.2% increase and insulin dose increase at any visit will also be summarized descriptively (for categorical measures) together to explore treatment sequence group difference.

An individual data listing will be provided for the patients with increase over 10% cross reacting antibody increase in both assays, of HbA1c over 0.2% increase and insulin dose increase at Week 12, 24 and 36.

The observed and Change values of HbA1c, Insulin dose, Cross reactive antibodies (Both assays) Fasting blood glucose, Subject's age, Duration of diabetes and Adverse events reported will be presented in the listing.

Presence of anti-HCP antibodies in samples from patients will be assessed using a validated immunoassay method. The results will be presented as positive or negative from anti-HCP antibodies based on the samples that HCP assay was done. Frequency and percentage of presence of anti-HCP antibodies will be presented at scheduled visits by treatment sequence group. The p-value from Fisher's exact test will be presented to test the difference between the treatment sequence groups for scheduled visits.

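### Protocol 7.2.5 ends insulin-dose recording at week 24, but the diary rules, SMBG schedule and SAP carry it to week 36

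*Protocol*

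**What the plan says.** Protocol 7.2.5 (Daily Insulin Doses) has patients document their glargine or Lantus dose and their lispro dose "on the days when they perform 8-point SMBG profiles (from week 0 to week 24").

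The other current text on the same data reads differently:

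- Protocol 7.5.5 (Patient Diary) lists basal doses and "mealtime insulin doses on days where a 8-point SMBG is performed", with no end week.
- Protocol Appendix IV lists "Insulin dose information on days where 8-point SMBGs are performed", again with no end week.
- Protocol Table 3 makes the 3-day 8-point profile mandatory for the "Week 0 to week 36 visits". The Schedule of Activities agrees: SMBG profiles are reviewed through V13 (week 36), and diaries are dispensed through V12 and reviewed through V13.
- Protocol 9.8 analyses "Daily prandial insulin, basal insulin, and total insulin dose (U/kg) for days of 8-point profiles".
- SAP 15.2.1.4 carries nearly the same sentence as protocol 7.2.5, but with the window "on the days when they perform 8-point SMBG profiles (from week 0 to week 36").

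The SAP's secondary objectives (section 2.2) are compared at 36 weeks, and the first in the list is "Change in basal insulin dose per unit body weight (U/Kg/day").

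**The concern.** The section that site staff would consult on dose recording closes the window at the end of period 2, while the analysis needs doses to the end of period 3. One site could stop recording at week 24 on the strength of 7.2.5, and another could continue on the strength of 7.5.5.

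Three planned outputs depend on period-3 doses:

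- the dose MMRM across scheduled visits (SAP 15.2 and 15.2.3.4), in particular its week-26 to week-36 contrasts;
- the correlation of cross-reactive antibodies with insulin dose (SAP 17.6.2);
- the individual listing of patients with rises in antibody, "of HbA1c over 0.2% increase and insulin dose increase at Week 12, 24 and 36".

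Period 3 follows the third transition in the design, which is the one that completes the switching pattern described in protocol 1.1. The trial is open-label and allows some titration in both arms, so dose in that period helps show whether similar HbA1c was reached with similar insulin use. SAP 7.3 does not impute missing secondary data.

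**Working it through.** The plan gives no figure of its own on this point, so the check is a comparison of texts followed by a count.

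**1. Can the texts be reconciled?** The parenthesis in 7.2.5 can be read in two ways.

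- *As a limit on dose recording.* It then conflicts with 7.5.5 and Appendix IV, which tie dose recording to every 8-point SMBG day, and directly with SAP 15.2.1.4.
- *As a description of when SMBG profiles are done.* It then conflicts with Table 3 and the Schedule of Activities, which run the profiles to week 36.

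Neither reading makes week 24 correct. SAP 3.3, which lists changes from the protocol, does not mention this window. Protocol section 12 allows protocol changes only by written amendment, so the SAP wording does not alter what 7.2.5 tells sites to do.

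**2. What falls outside the window?**

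- Post-baseline clinic visits (Schedule of Activities): weeks 2, 4, 8, 12, 14, 16, 20, 24, 26, 28, 32, 36 = 12 visits.
- Visits after week 24: weeks 26, 28, 32, 36 = 4. Share: 4/12 = 33%.
- Diary days per visit: 3 (Schedule footnote and protocol 7.2.4). Total 12 × 3 = 36; outside the window 4 × 3 = 12.
- Across 138 patients: 138 × 12 = 1,656 patient-days. With the plan's 10% allowance applied, 138 × 0.9 ≈ 124 patients and 124 × 12 = 1,488 patient-days.

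**3. How much might be lost?** Let *f* be the share of patients at sites that apply 7.2.5 literally. The documents give no value for *f*, so the range below is assumed.

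- Patient-days lost = *f* × 1,656.
- Width of a week-36 confidence interval from observed values only, relative to full data = 1/√(1 − *f*). This takes the loss as equal in the two arms.

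| *f* (assumed) | Patient-days lost | Relative CI width |
|---|---|---|
| 0% | 0 | 1.00 |
| 10% | 166 | 1.054 |
| 25% | 414 | 1.155 |
| 50% | 828 | 1.414 |

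The planned MMRM borrows information from earlier visits. With balanced loss its interval should therefore widen by less than the last column shows. If loss is unbalanced between arms, that column is not a bound.

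**4. What is untouched?** The primary endpoint is HbA1c and uses no dose data. The sample size rests on the HbA1c standard deviation and margin alone.

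**The case against.** The best defence is that the working parts of the protocol already cover period 3. The Schedule requires dose review at every visit through V12, and the diary runs to week 36. Protocol 7.2.5 itself goes on, with no week limit, to ask for the three pre-visit doses. The sponsor supplies one diary, all sites use one validated eCRF system, and monitors check completeness. A common form would tend to produce the same collection everywhere. On this view the number is a leftover that nobody would act on, and the loss scenarios are conjecture. Table 3 also says nothing about doses; it bears on the point only together with 7.5.5 and Appendix IV.

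Much of this stands. Complete collection is quite possible, the values of *f* are assumptions, and Table 3 does not contradict 7.2.5 on dose recording by itself. Being first in the list of secondary objectives also confers no formal priority, since the plan sets no hierarchy and makes no multiplicity adjustment.

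It does not remove the conflict. The wrong number is in the section that defines the assessment. The dose-review row of the Schedule stops at V12, which leaves the diary as the planned source of daily doses at week 36. Whether the V10–V13 diary and eCRF pages contain dose fields cannot be seen from the documents. If those forms were built from 7.2.5, a common design would spread the gap to every site.

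**Conclusion.** The concern holds. The recording window in protocol 7.2.5 contradicts protocol 7.5.5 and Appendix IV (read with Table 3 and the Schedule) and SAP 15.2.1.4. Followed literally, it removes every period-3 dose record: 4 of 12 post-baseline visits, or 12 of 36 diary days per patient, including the week-36 endpoint of a named secondary objective.

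The visit and day counts follow from the documents. The realised loss does not: it ranges from none upward with the assumed *f*, and the interval widths further assume balanced loss and an observed-values analysis. This is a risk of missing or site-dependent secondary data, not a demonstrated loss. It should be fixed, but it does not threaten the primary conclusion.

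**What to change.** In protocol 7.2.5, change the end of the window from week 24 to week 36, or delete the window and refer to the Schedule of Activities, so that the section agrees with 7.5.5, Appendix IV, Table 3 and SAP 15.2.1.4. Confirm that the period-3 diary and the V10–V13 eCRF pages carry fields for both the basal and the lispro dose. If period 3 is already under way, check the completeness of its dose data by site and by sequence group.

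The cost is one corrected number, issued as a written amendment, and a check of the forms. Patients do nothing extra, because profiles and diaries already run to week 36. The change concerns data recording only and sets no dose.
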